7.2.3 Withdrawal from Study Criteria

Reasons for discontinuation of study medication include, but are not limited to, the following:

- Adverse Event
- Pregnancy
- Withdrawal By Subject
- Lost To Follow-Up. The Investigator will try to reach the subject, twice by telephone (document telephone calls) and once by certified letter, before considering the subject lost-to-follow-up. The lost to follow-up discontinuation will be reported on the appropriate eCRF, and a copy of the follow-up letter will be maintained in the Investigator's file.
- Study Terminated By Sponsor
- Physician Decision
- Non-Compliance with Study
- Other

CONFIDENTIAL

Version Date: 10 July 2015

All premature discontinuations from the study must be documented by the Investigator on the eCRF, and if due to an adverse event, on the Adverse Event Case Report page of the eCRF. All subjects should attempt to complete all visits and evaluations.

Subjects not completing the entire study should be fully evaluated (i.e., final double-blind Week 12 visit procedures performed during the double-blind period and the Follow-up Week 16 visit procedures during the follow-up period). All subjects are free to withdraw from participating in this study at any time and for whatever reason, specified or unspecified, and without prejudice to his or her medical care by a physician. Subjects who withdrawal from the study will not be replaced.

CONFIDENTIAL

Version Date: 10 July 2015

7.3 CONDUCT OF STUDY

7.3.1 Table of Study Procedures

Procedures	Screening (Within 30 days of Baseline)	Baseline/Day 1 (prior to study drug application)	Interim Visits: Weeks 1, 3, 6 and 9 (\pm 3 days)	Final Double- Blind Visit: Week 12 (\pm 3 days)	Follow-Up Visit: Week 16 (\pm 3 days) ⁴
Informed Consent	X				
Demographics, Medical and Rosacea History	X	X			
Previous Medications	X				
Concomitant Therapy/Medication Review	X	X	X	X	X
Limited Physical Exam	X			X	
Vital Signs	X		X (week 6 only)	X	X
Blood collection for clinical laboratory testing	X			X	
Blood collection for immunogenicity testing		X	X (week 3 &6)	X	X
Urine Pregnancy Test, if applicable	X			X	
Investigators Global Assessment (IGA)	X	X	X	X	X
Investigators Assessment of Erythema (IAE)	X	X	X	X	X
Other Signs and Symptom Assessment	X	X	X	X	X
Inflammatory Lesion Counts	X	X	X	X	X
Inclusion/Exclusion Criteria	X	X			
Randomization		X			
Dispense Study Drug		X	X ¹		
Dispense Diary		X	X		
Drug Accountability / diary review, and Collection of Drug and diary			X	X	
Instruct on Treatment Application		X			
Apply Study Drug ²		X ²	X	X	
Adverse Event Assessment		X ³	X	X	X

¹ Study drug will not be dispensed at the Week 1 visit. .² The first application of study drug will be performed at the study center.³ Adverse event assessment during the Baseline visit will be performed following the first application of study drug.⁴ The end of the study will be the date that the last study subject completes the last visit for the study.

CONFIDENTIAL

Version Date: 10 July 2015

7.3.2 Study Procedures by Visit

Visits following the Baseline Visit are to occur at the end of Weeks 1, 3, 6, 9, and 12 (Final Treatment Visit) and a follow up visit at Week 16. However, all interim study visits and the follow up Week 16 study visit may be conducted (on an individual subject basis) up to 3 days before or after the regularly scheduled study visit. An unscheduled visit may occur in the event that the investigator determines that the subject should be seen for safety or any other reasons.

7.3.2.1 Screening Visit

The following procedures will be performed during the Screening visit:

- Obtain subject's written informed consent prior to initiating any study procedures, including instructing the subject to discontinue use of medication that requires a washout (see Section 7.6.11.1). Provide subject with a copy of signed and dated consent form. Document subject's informed consent in the subject's medical record.
- Screen the potential subject according to the study inclusion/exclusion criteria.
- Schedule the Baseline/Day 1 visit to occur after the results of the laboratory safety testing are received and any required washout period is completed.
- Record Demographic information including age, sex, race, ethnicity and Fitzpatrick skin type (Appendix B)
- Record medical history. Include information on subject's history of rosacea and any previous therapies, including:
 - The approximate date of physician's diagnosis of rosacea;
 - The subject reported signs and symptoms of rosacea,
 - How often they experience these symptoms?
 - Whether symptoms are continuous or occasional?
 - What, if anything, appears to trigger or worsen these symptoms?
 - Sunlight
 - Stress
 - Alcohol
 - Exercise
 - Hot and cold temperatures
 - Spicy food
- Previous rosacea therapies within the previous 5 years;
- Review and record concomitant medications/therapies used in the last 30 days
- Assess whether the subject will require a washout period
- Perform a limited Physical Exam (refer to Section 7.5.2) with vital signs, height and weight measurements.
- Obtain a blood sample for hematology and chemistry analysis
- Perform an in-office urine pregnancy test on all females of childbearing potential.
- Perform the Investigators Global Assessment (IGA) of rosacea, the Investigators Assessment of Erythema (IAE) and Other Signs and Symptoms Assessment before performing the lesion count (refer to Section 7.4.1, 7.4.2, and 7.4.3). **It is important that the same evaluator performs the evaluations for the same subject at each visit, however it may not be**

CONFIDENTIAL

Version Date: 10 July 2015

feasible in all instances. Every effort should be made to maintain consistency of the evaluator for each subject.

- Perform the inflammatory lesion count (papules and pustules) (refer to Section 7.4.4). **It is important that the same evaluator performs the lesion count for the same subject at each visit, however it may not be feasible in all instances. Every effort should be made to maintain consistency of the evaluator for each subject.**

7.3.2.2 Baseline Visit (to be scheduled within 30 days of Screening)

- Review the study inclusion/exclusion criteria to confirm eligibility, including review of the laboratory results for any clinically significant findings that would exclude the subject from eligibility for the study.
 - Review any changes since the first visit in concomitant medications/therapies, and the subject's health.
 - Perform the Investigators Global Assessment (IGA) of rosacea, the Investigators Assessment of Erythema (IAE) and Other Signs and Symptoms Assessment before performing the lesion count (refer to Section 7.4.1, 7.4.2, and 7.4.3). **Every effort should be made to maintain consistency of the evaluator for each subject.**
 - Perform the inflammatory lesion count (papules and pustules) (refer to Section 7.4.4). **Every effort should be made to maintain consistency of the evaluator for each subject.**
 - If the subject has fulfilled the eligibility requirements, as stated in the inclusion/exclusion criteria, randomize the subject to treatment according to the randomization instructions using the eDC system to access the Interactive Web Response System (IWRS). The eDC/IWRS system will generate the kit number assigned to the randomized subject for the duration of the study. The subject's assigned kit number should match the kit number on all drug treatment supplies dispensed to the subject. Record the subject number on the kit that is assigned to that subject.
 - Record the assigned kit number and the subject number on the source document.
 - Obtain the Pre-Dose blood sample for immunogenicity testing prior to the first application of study gel.
- First Treatment Application –
 - Weigh the tube that is designated to be dispensed to the subject prior to the subject applying their first dose of study medication. The tube should be weighed with the cap on as outlined in Section 7.6.9.
 - Give the subject a copy of the treatment application instructions (see Appendix A) and allow the subject to take time to read them. Provide instruction to the subject on the daily application of study drug and confirm the subjects understanding of the instructions.
 - Record the Subject # and date of dispensing on the tube label and dispense the tube to the subject.
 - The subject should be instructed to apply the treatment once daily, preferably each morning (with the exception of the first dose at the site which may be later in the day), at approximately the same time for the duration of the study. A thin layer of the assigned study drug (approximately 0.4 g) should be applied to the subject's face, including the non-affected areas (as described in Appendix A).

CONFIDENTIAL

Version Date: 10 July 2015

- Under the supervision of the study coordinator or designee, the subject should apply the first dose of study drug at the study site and the observer should observe that the subject applies a thin film to the entire face.
- Instruct the subject on the use of the daily diary and dispense the diary.
 - Have the subject record the first application of study drug in the diary during the site visit and confirm their understanding of the use of the diary.

After the first application of study drug at this visit -

- Observe the subject for any immediate adverse events.
- Remind the subject about restricted therapies (see Section 7.6.11.1).
- Remind subject to contact the investigator if he/she experiences any adverse events.
- Remind subject that the study drug tube is not to be discarded and that the drug tube must be returned to the site at the next study visit. Subjects should be instructed to immediately report a lost tube to the site.
- Remind the subject to apply the study drug once daily, as directed, preferably in the morning.
- Remind the subject to record their study drug application in the diary each day during the study and to return the diary to the site at the next study visit.
- Remind subjects to follow the treatment instructions.

7.3.2.3 Interim Visits Week 1, 3, 6, and 9 (± 3 days)

- Question the subject about any new or changes in adverse events
- Question the subject about any new or changes in concomitant medications/therapies.
- Obtain vital signs at Week 6 visit ONLY.
- Obtain a blood sample for immunogenicity testing at Week 3 and Week 6.
- Perform the Investigators Global Assessment (IGA) of rosacea, the Investigators Assessment of Erythema (IAE), and Other Signs and Symptoms Assessment before performing the lesion count (refer to Section 7.4.1, 7.4.2, and 7.4.3). **Every effort should be made to maintain consistency of the evaluator for each subject.**
- Perform the inflammatory lesion count (papules and pustules) (refer to Section 7.4.4). **Every effort should be made to maintain consistency of the evaluator for each subject.**
- The subject should apply the study drug at the study site under supervision of the study coordinator or designee
- **Treatment Compliance Check** - Collect the diary to perform a treatment application compliance review. Check compliance by reviewing the number of treatment applications in the diary to determine if there are missed doses. The subject should be re-instructed on study drug application, if compliance is an issue.
- Collect the previous diary and dispense a new diary to the subject at the Week 3, 6, and 9 Visits. The diary reviewed at the Week 1 Visit should be returned to the subject for use until the Week 3 Visit. The Week 9 Visit diary should be collected at the Week 12 Visit.
- **Dispensing and Return of Study Treatment** - No new study drug supply will be dispensed at the Week 1 visit; the drug tube which was dispensed to the subject at Baseline should be returned to them at Visit 1 after completing the treatment application compliance check. **Collect the old study medication tube and dispense a new tube of study medication after weighing it at the Week**

CONFIDENTIAL

Version Date: 10 July 2015

3, 6, and 9 Visit. Record the date of dispensing on the tube label. Weigh returned tubes. The dispensing and return information should be recorded on the source document.

- Remind the subject about restricted therapies (see Section 7.6.11.1).
- Remind the subject to apply the study drug once daily, as directed, preferably in the morning and record their daily treatment application in their diary.
- Remind the subject to contact the investigator if he/she experiences any adverse events.
- Remind subject that the study medication tubes are not to be discarded and all must be returned to the site at the next study visit. Remind them to notify the site immediately if they have lost a tube.
- Remind the subject to return the diary to the site at the next study visit.
- Remind the subject to follow the treatment instructions.

7.3.2.4 Final Double-Blind Treatment Visit (Week 12) (\pm 3 days)

- Question the subject about any new or changes in adverse events.
- Question the subject about any new or changes in concomitant medications/therapies.
- Perform the Investigators Global Assessment (IGA) of rosacea, the Investigators Assessment of Erythema (IAE) and Other Signs and Symptoms Assessment before performing the lesion count (refer to Section 7.4.1, 7.4.2, and 7.4.3). **Every effort should be made to maintain consistency of the evaluator for each subject.**
- Perform the inflammatory lesion count (papules and pustules) (refer to Section 7.4.4). **Every effort should be made to maintain consistency of the evaluator for each subject.**
- Perform a limited Physical Exam with vital signs and weight measurement.
- Obtain a blood sample for hematology and chemistry analysis.
- Obtain a blood sample for immunogenicity testing.
- Perform an in-office urine pregnancy test on all females of child-bearing potential.
- The subject should apply the study drug at the study site under supervision of the study coordinator or designee
- **Treatment Compliance Check** - Collect the diary to perform a treatment application compliance review. Check compliance by reviewing the number of treatment applications in the diary to determine if there are any missed doses.
- **Drug Return** -All double-blind study drug tubes should be collected by the Week 12 treatment visit. The weight of the tubes at dispensing and return should be documented. Any missing tubes must be documented.
- Remind the subject to contact the investigator if he/she experiences any adverse events.
- Remind the subject about restricted therapies (see Section 7.6.11.1).

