Additionally, the systemic absorption of omiganan pentahydrochloride topical gel has been evaluated at concentrations of 0.5%, 1%, 2.5% and 3%. Omiganan was not systemically absorbed when applied to the skin of subjects at concentrations ranging from 0.5% to 3% topical. In the most recent maximum use PK study of omiganan pentahydrochloride topical gel 2.5% w/w, applied for 21 days to the face of 26 subjects with moderate to severe papulopustular rosacea, no systemic absorption was detected. The results of the clinical studies and the safety data collected during the clinical studies of omiganan are summarized in the Investigator's Brochure.

Omiganan Topical gel [REDACTED] in this protocol, in previously conducted phase 1 and 2 clinical studies, and in other historical documentation is based on the concentration of omiganan pentahydrochloride. The product concentration based on the active moiety is omiganan topical gel [REDACTED]. To be consistent with the naming convention in pre-existing documents, the nomenclature concentration of omiganan [REDACTED] will be referred to in this protocol and associated clinical and non-clinical documents.

[REDACTED]

Further, in order to comply with USP General Chapter <1121> Nomenclature to express the strength of the drug product based upon the active moiety, [REDACTED]

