7.4.2 Investigators Assessment of Erythema (IAE)

The IAE should be performed at screening and each visit (Baseline, Weeks 1, 3, 6, 9, 12, and 16) prior to performing the lesion count using the scale below. The IAE is intended for the global evaluation of erythema of rosacea. This is an assessment of nontransient erythema, or background erythema. Telangiectasias are assessed separately as described under section 7.4.3.

Investigators Assessment of Erythema (IAE) Scale

Grade	Grading Scale Score	Description of Background Erythema
Clear	0	No redness present. Background erythema is consistent with non-involved areas.
Almost Clear	1	Slight and localized background erythema in involved areas of the face, usually limited to the malar prominence of the cheeks. Gives the impression of a healthy glow to the cheeks.
Mild	2	Slight to mild background erythema NOT limited just to the cheeks, but extends to the lateral cheeks, chin, or forehead.
Moderate	3	Definite background redness, easily recognized, and extending to lateral cheeks, chin, or forehead.
Severe	4	Severe background erythema over the entire face.

The IAE rating of erythema is considered as part of the baseline assessment. If a worsening of erythema from Baseline is believed by the investigator to be related to the study drug and not the disease, then it should be recorded as an AE.

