7.5.2 Limited Physical Exam and Vital Signs

A limited physical exam will be performed at the Screening Visit (including height and weight) and at the final Week 12 Visit (End of Treatment Visit or Early Termination Visit), including weight will be performed. The limited Physical Exam should include an assessment of the following:

- General Appearance
- Head
- Eyes
- Ears
- Nose
- Throat
- Lungs
- Heart
- Skin

CONFIDENTIAL

Version Date: 10 July 2015

Vital signs (blood pressure, respirations, heart rate) will be measured at the Screening Visit, Week 6, Week 12 (Final or Early Termination) Visit and at the Week 16 (Follow up) Visit.

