8.5 PROTOCOL ADHERENCE

The Investigator must read the protocol thoroughly and must follow the instructions exactly. Any change should be agreed upon by prior discussion between the CRO/Sponsor and the Investigator, with appropriate written protocol amendments made prior to implementation of the agreed-upon changes. Any amendment containing major modifications (particularly if it may involve an increased risk to the subjects) will be approved by the IRB/IEC before it may be implemented.

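### The early-termination visit inherits a supervised study-drug application from the Week 12 procedures, with no stated exception for subjects who have stopped the drug

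*Protocol*

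**What the plan says.** Protocol 7.2.3 opens with a list headed "Reasons for discontinuation of study medication include, but are not limited to, the following". Adverse event and pregnancy are both on it. The same section then sets the rule for the last visit: "Subjects not completing the entire study should be fully evaluated (i.e., final double-blind Week 12 visit procedures performed during the double-blind period", with the Week 16 procedures used instead for those who leave during follow-up.

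Protocol 7.3.2.4 lists the Week 12 procedures. After the efficacy assessments, physical examination, blood samples and pregnancy test comes the bullet "The subject should apply the study drug at the study site under supervision of the study coordinator or designee". No condition is attached. In the schedule at 7.3.1, the "Apply Study Drug" row is marked at Week 12, and its only footnote concerns where the first application takes place.

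Other sections confirm that the Week 12 visit doubles as the early-termination visit. Section 7.5.2 refers to the "final Week 12 Visit (End of Treatment Visit or Early Termination Visit"), and 7.5.3 and 7.5.5 use similar labels for the laboratory and pregnancy tests. SAP 6.1 also treats a non-completer's last double-blind visit as a Week 12 visit, which it then reassigns by study day. Section 7.5.5 requires that a subject who becomes pregnant be withdrawn.

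**The concern.** A subject who has stopped study medication should not be given it again at the exit visit. The cross-reference in 7.2.3 takes over the whole Week 12 list, and that list contains a dose.

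The case that matters is a subject who stops because of a local reaction. The protocol foresees such reactions: in 7.4.2, the condition for recording an adverse event begins "If a worsening of erythema from Baseline is believed by the investigator to be related to the study drug and not the disease", and 7.4.3 has a parallel rule for the other signs and symptoms. Under a literal reading this subject applies the gel to the entire face again, at a visit held because the gel was not tolerated. The dose serves no measurement, since the efficacy assessments come earlier in the list. At Baseline, staff are told to watch for immediate adverse events after the application; the Week 12 list has no such step.

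Section 8.5 makes the literal reading harder to set aside: "The Investigator must read the protocol thoroughly and must follow the instructions exactly". A site that sensibly skips the application departs from a listed procedure, and a site that follows the list re-exposes the subject.

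**Working it through.** The plan gives no figure to reproduce. The check is a cross-reading of the sections, followed by a short calculation of the size of the exposure.

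**The chain of instructions**

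1. *Who is covered.* Section 7.2.3 covers subjects who do not complete the study. Those who leave in the double-blind period get the Week 12 procedures.
2. *What those procedures contain.* Section 7.3.2.4 and the Week 12 column of 7.3.1 both include the application.
3. *Whether an exception exists.* None appears in 7.2.3, 7.3.2.4, the 7.3.1 footnotes, 7.5.2, 7.5.3, 7.5.5, or the available parts of 7.6. Elsewhere the protocol does state exceptions when it wants them. A 7.3.1 footnote says no drug is dispensed at Week 1, and 7.3.2.3 limits interim vital signs to Week 6.
4. *Whether the pregnancy test controls the application.* In 7.3.2.4 the test comes directly before the application, but the application is not made conditional on its result. By contrast, 7.2.1 and 7.5.5 require a negative test before randomization.
5. *Where the conflict lies.* Steps 1 to 3 end in a dose for a subject whom the list in 7.2.3 describes as having discontinued study medication. For pregnancy, they also sit badly with the withdrawal rule in 7.5.5.

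**Who is not affected**

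- Subjects who leave during follow-up: the Week 16 list in 7.3.2.5 has no application.
- Subjects lost to follow-up: there is no visit.
- Subjects who complete treatment: the Week 12 application is part of their course.

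**Size of the exposure**

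Inputs: once-daily application of about 0.4 g for 12 weeks (7.6.1).

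- Planned applications: 12 weeks × 7 days = 84
- Planned course: 84 × 0.4 g = 33.6 g
- One further application: 0.4 / 33.6 = 1/84 = 1.2% of the course

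**Number of subjects**

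This cannot be derived. Neither document gives a discontinuation rate, overall or by reason.

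**Effect on efficacy data**

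In 7.3.2.4 the IGA, erythema, signs-and-symptoms and lesion-count assessments are all listed before the application. What is recorded at that visit therefore does not depend on the extra dose.

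**The case against.** The strongest reply is that the protocol already answers the question in context. The rule sits under a list of reasons for discontinuing study medication, and a subject who has discontinued is off the drug. The rule says such subjects are to be evaluated, and applying gel is not an evaluation. Every place that equates Week 12 with early termination (7.5.2, 7.5.3, 7.5.5) does so for an assessment. The application bullet says 'should' and stands under a title written for subjects still on treatment. The instruction in 8.5 to follow the protocol exactly covers the discontinuation and withdrawal rules as much as the visit checklist.

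Most of this stands as evidence of intent, and most clinicians would not re-dose. It does not remove the defect. The wording in 7.2.3 explains the evaluation by pointing to the Week 12 procedures as a whole, without limiting them to assessments, and the reader must infer an exception that could be stated in a few words.

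A reader might infer three stronger points that the documents do not support:

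- *That the protocol tells sites to dose pregnant subjects and so exposes a fetus.* Section 7.5.5 points the other way by requiring withdrawal. Section 5.1 reports that in a maximum-use study of the 2.5% gel, "applied for 21 days to the face of 26 subjects with moderate to severe papulopustular rosacea, no systemic absorption was detected". Pregnancy matters here only as an inconsistency between two rules.
- *That a known number of subjects would be re-dosed.* Any count would rest on an assumed rate of stopping, of attending the visit and of sites following the list literally. Section 5.1 also describes the product as well tolerated in earlier studies, which gives no basis for such a rate.
- *That the primary comparison is biased.* The order of procedures at the visit gives no support for this.

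One limit applies to the check itself. Part of 7.6.1 to 7.6.3 is missing from the text available for review, so an exception there cannot be ruled out. It is unlikely, because those sections cover administration, product identity and treatment assignment.

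**Conclusion.** The point holds as a missing explicit exception. Taken literally, 7.2.3 together with 7.3.2.4 and 7.3.1 asks a subject who has stopped study drug to apply it once more, which conflicts with discontinuation for an adverse event and with withdrawal for pregnancy. The probable intent is assessment only.

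The consequence is small: one application of about 0.4 g per affected subject, relevant mainly to someone who stopped for a local facial reaction. The number affected is unknown, and efficacy results are unaffected.

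This conclusion rests on the available text containing every relevant instruction, and on a site following the list as written. SAP 5.4.2 and 7.0 record that enrollment was discontinued after the interim analysis. The practical value therefore lies with any subjects still on treatment and with any reuse of this text; protocol 7.7.2 refers to two Phase 3 studies. Minor; a free improvement.

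**What to change.** - In 7.2.3, replace the reference to the Week 12 visit procedures with: *Week 12 assessments, without study drug application*.
- In 7.3.2.4, and as a footnote to the "Apply Study Drug" row of 7.3.1, add: *Study drug is not applied at an early-termination visit, after permanent discontinuation of study drug, or after a positive pregnancy test.*
- Leave the Week 12 application in place for subjects who complete treatment.

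The cost is one phrase, one sentence and one footnote. No procedure is added, and no endpoint, sample size or analysis changes.
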